6.2. In- and exclusion criteria for follow-up assessment

The investigator will ensure that all patients considered for the study meet the inclusion and exclusion criteria described in Sections 6.2.1 and 6.2.2.

6.2.1. Inclusion criteria

- 50–95 years of age.
- Diagnosis of PD according to the United Kingdom Brain Bank criteria.
- Ability to communicate well with the investigator, to understand and comply with the requirements of the study.
- Provide written informed consent to participate in the study and understand the right to withdraw consent at any time without prejudice to future medical care.

6.2.2. Exclusion criteria

- Any disability that may prevent the subject from completing the informed consent form or other study requirements.
- Other neurodegenerative disease which renders the subject unable to communicate well with the investigator or to understand and comply with the requirements of the study.
- Participation in any clinical investigation of a new investigational compound or therapy within 4 weeks prior to baseline visit, and any other limitation of participation based on local regulations.
- Alcohol, medication, or drug dependency or abuse (except for nicotine).
- History of brain disease other than PD, e.g., head trauma, stroke, encephalitis.

6.3. Recruitment

Participants of the already recruited ABC-PD cross-sectional cohort (ethic protocol: 284/2018BO1) will be asked to participate in the follow-up assessment. Patients who did not agree to participate in a longitudinal study or who have asked not to be contacted after the first cross-sectional assessment will not be contacted again. A drop-out rate of 20% is expected for follow-up retention. Therefore, investigation of 145 patients will be primarily conducted between January 2023 and June 2024. During the executive project phase, around 7 to 9 patients will be assessed per month. Patients will be contacted either via phone or in written form. Reasons for drop-outs will be registered for data analysis.

7. Statistics and Sample size estimation

All following hypotheses will be tested a priori; no post-hoc corrections of p-values will be conducted.

Characterization of study groups: Between-group comparisons at clinical visits will be conducted using Mann-Whitney-U or Welch test (two groups) or Jonckheere-Terpstra test (>2 groups) for numerical variables and χ^2 test or Exact Fisher Test for categorical variables. Post-hoc comparisons for IADL and cognitive variables between groups will be corrected for between-group covariates via linear regression models with group status as dummy coded variable. When follow-up cognitive groups are compared (PD-CN vs. PD-MCI vs. PDD), analyses with covariates will be run twice with reference category set as either PD-CN or PD-MCI.

Prediction of cognitive progression along with progression in ADL function over time: In patients who completed all visits, the predictive values of baseline/follow-up IADL (patients' self-impression vs. informant-rating), stratification (cognitive IADL impairment vs. motor IADL impairment), cognitive status (PD-CN vs. PD-MCI), and both markers combined (PD-MCI + cognitive IADL impairment) will be calculated using multivariate Cox Proportional-Hazard models. Akaike's information criterion (AIC) and concordance index (C-index) [26] will be used as model fit indices. Logistic regression with follow-up cognitive diagnosis (PD-CN vs. PD-MCI or non-demented vs. PDD) as dependent variable will evaluate whether baseline status of cognitive IADL impairment (FAQ quotient >1.008) predicted risk of PDD conversion independent of other clinical variables (e.g., cognitive status), biomarker profile, and covariates. As a post-hoc exploratory analysis to identify which subscore best predicted PDD conversion, ROC curves will be calculated for all FAQ scores (self- and caregiver-assessment). The optimal score/cut-off will be chosen according to the highest Youden Index. Linear regression will be applied to investigate predictors of neuropsychological scores and IADL measures at follow-up(s).

2. Defining the interaction of progression in markers over time

Generalized linear mixed effects models (GLMMs) will evaluate progression in neuropsychological tests and IADL scores over time. Correlation analyses are planned to investigate association in change of scores over time of different measures.

Sample size calculation:

Between the baseline and first follow-up 17 (10.4%) patients developed PDD within a mean follow-up interval of 3.78 ± 0.84 years (range: 1.67-5.79 years), with higher rates of converters in patients with baseline status of cognitive ADL impairment (29.7%). Estimated follow-up interval between first and second follow-up are expected to be very similar, and a higher rate of patients with cognitive ADL impairment were identified. Moreover, the risk for PDD development is increased in later disease stages [27, 28]. Therefore, a maximum of additional 15 converters are expected.

Monte Carlo simulation-based calculations of observed power (R package simr, version 1.0.6), revealed a minimum sample size of $n = 64$ (Power = 94.00%; 95%-CI: 83.45-98.75) to detect the three-way interaction in the GLMM evaluation of the progression in the FAQ total score in different study groups (e.g., PD-NC vs. PD-MCI), and of $n = 71$ (Power = 92.00%; 95%-CI: 80.77-97.78) for the three-way interaction in the GLMM evaluating progression of FAQ motor score.

8. Assessments

The explanation of study requirements and informed consent will be conducted as first procedure.

Table 1: Overview of clinical in-house assessments and assessments which can alternatively be assessed within an additional phone interview.

Assessment of PD patients	Time
Explanation of the study requirements	10 min
Informed written consent	5 min
Neurological assessments:	
Medication intake, concomitant diseases and procedures	10 min
Unified Parkinson's Disease Rating Scale (UPDRS) Parts III-IV, Hoehn & Yahr Stage*	15 min
Cognitive test battery:	
Montreal Cognition Assessment (MoCA)	10 min
Mini Mental State Examination (MMSE)	5 min
Consortium to Establish a Registry for Alzheimer's Disease (CERAD-Plus, German Version)	25 min
Trail Making Test Parts A and B	10 min
Fragmented Words (Subtest of the Leistungsprüfsystem für 50- bis 90-Jährige, LPS 50+)	5 min
Digit-Symbol Test (Subtest of the Wechsler Intelligenztest für Erwachsene, WIE)	5 min
Similarities (Subtest of the WIE)	5 min
Letter-Number Sequencing (Subtest of the WIE)	5 min
Pill-Questionnaire	5 min
Total time of mandatory in house assessments	115 min
Optional: Dementia Apraxia Test (DATE)	5 min
Optional: Kölner Apraxie Screening	8 min
Total maximum time of optional in house assessments	13 min
Assessments, which can be alternatively assessed within an additional phone interview	
Demographics & lifestyle	
Age, gender, education, occupation, family history of neurodegenerative diseases, smoking/drinking behavior, height & weight#	5 min
PD Non-Motor Symptom Scale, subscales 1-5 (PD-NMS-S) #	5 min
Unified Multiple System Atrophy Rating Scale (UMSARS) I: History of autonomic symptoms#	2 min
History and self-awareness of cognitive deficits#	5 min
Total maximum time of additional phone interview	17 min

Legend: *: For patients with an appointment in the outpatient clinic data will be assessed within the frame of the clinical daily routine;
#: Information can be assessed within the frame of phone interview

Table 2: Overview of clinical assessments conducted at home by study patients

Patient questionnaires (filled out at home):	
Parkinson's Disease Non-Motor Symptoms Questionnaire (PD-NMS-Q)	3 min
Beck Depression Inventory – II (BDI-II)	5 min
Beck Anxiety Inventory (BAI)	2 min
Pfeffer Functional Activities Questionnaire (FAQ)	2 min
Parkinson's Disease Activities of Daily Living Scale	1 min
Parkinson's Disease Questionnaire (PDQ-39)	5 min
Freezing of Gait Questionnaire (FOG)	1 min
Epworth Sleepiness Scale (ESS)	2 min
REM Sleep behavior questionnaire (RBDS-Q)	2 min
Apathy Evaluation Scale (AES)	3 min
Skala zur Allgemeinen Selbstwirksamkeitserwartung (SWE)	5 min
Questionnaire for Impulsive-Compulsive Disorders in Parkinson's Disease-Short (QUIP-Kurz)	3 min
Unified Parkinson's Disease Rating Scale (UPDRS) Parts I-II	6 min
International Consultation on Incontinence Questionnaire-Short Form (ICIQ-SF)	2 min
Patient Perception of Bladder Condition (PPBC)	1 min
Total time of clinical assessment conducted at home by patients:	43 min
Optional: Home-based movement assessment (accelerometry device)	7 days

The Kölner Apraxie Test included for validation of the Dementia Apraxia Test (DATE) as well as the Skala zur Allgemeinen Selbstwirksamkeitserwartung (SWE) will be applied as additional study outcome. All other scales and measurement were also included in the first follow-up of the sample (Title: Cognitive driven ADL impairment as a predictor for PDD; ethic protocol: 284/2018BO1). For this scientific study, all investigations will be performed in an ambulatory setting and need the study participants to be available for at least 3 hours, not including the optional blood marker sampling.

If patients agree to the optional CSF and/or blood collection (see also 8.5):

- Blood collection 15 min
- CSF 30 min
- Bed rest after CSF collection 30 min

Total time for biomarker sampling: 75 min

Invasive biomarker sampling will not be conducted for patients, who are not able to give consent for study participation.

Caregiver assessments:

To validate the patients' self-impression, the following caregiver questionnaires and interview scales will be applied, needing caregivers to be available for at least 38 minutes. Caregiver assessments will only be performed if the respective patient has agreed to the interview.

Table 3: Overview of caregiver assessments

Assessment	Time
Explanation of the study requirements	10 min
Interview-based ratings:	
Informant Questionnaire on Cognitive Decline in the Elderly (IQ-CODE)	6 min
Questionnaires:	
Pfeffer Functional Activities Questionnaire (FAQ)	4 min
Bayer Activities of Daily Living Scale (Bayer ADL)	5 min
PD Angehörigen Belastungs- und Befindlichkeitsskala (PD-ABB-Scale)	8 min
Zarit Caregiver Burden Inventory (ZCBI)	5 min
Total Time of caregiver assessment:	38 min

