4.1. Hypothesis and research questions

Based on previous reports and preliminary results, we hypothesize that PD-MCI patients with a more pronounced cognitive-driven ADL impairment ($FAQ_{Q>1.008}$) are at higher risk for worsening in cognition and conversion to PDD than PD-MCI patients with ADL impairment primarily related to motor function ($FAQ_{Q\leq 1.008}$).

1. *Prediction of cognitive progression along with progression in IADL function over time*

- Aim 1.1: Prediction of conversion rates to PD-MCI (among PD-CN) and PDD (among non-demented patients) according to baseline IADL, cognitive, genetic, and biomarker profiles in blood and CSF
- Aim 1.2: Prediction of progression in cognitive scales according to cognitive, IADL, genetic, and biomarker profiles in blood and CSF
- Aim 1.3: Prediction of worsening in available ADL scales (patient-/informant-ratings) according to cognitive, IADL, genetic, and biomarker profiles in blood and CSF

2. *Defining the interaction of progression in markers over time*

- Aim 2.1: Evaluation of progression in varying cognitive tests assessed along with change in ADL function, non-motor markers and, if available, biomarker status
- Aim 2.2: Evaluation of progression in IADL function (patient-/informant-ratings) along with change in cognition, non-motor markers and, if available, biomarker status

5. Study duration

Total duration of the study is 2 years.

6. Study population

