8.5. Biomaterial collection

8.5.1. CSF and blood collection

Blood and CSF samples will be collected in the morning, on an empty stomach. If patients do not agree for a lumbar puncture, fasting for blood sampling is not necessary for biomarker analysis.

Blood collection: For patients with no CSF withdrawal about 40 ml venous blood will be collected for data analysis and storage of blood in the neurobank of the Hertie-Institut für klinische Hirnforschung (ethic proposal: 199/2011BO1). This amount does not represent any health hazard. For study related analysis of serum neurofilament light chain 10 ml of venous blood (1 Serum tube) will be collected. If the patient agrees for withdrawal of CSF additional 12,5 ml venous blood (2 serum tube, 1 NaF (glucose) 2,5 ml, total amount of venous blood 52,5 ml) will be taken for safety analysis in the Zentrallabor of the UKT.

Through venipuncture, the following samples will remain in the Hertie-Institut für klinische Hirnforschung (ethic proposal: 199/2011BO1):

- 20 ml of venous blood in 2 large EDTA tubes
- 10 ml of venous blood in 1 Serum tube

Blood in the Neurobiobank will be stored and used for targeted biomarker search, for explorative proteomic and metabolomics approaches, as well as for the determination of genetic markers in those without DNA analysis by using the NeuroChip (e.g. APOE Genotype, MAPT, COMT, and GBA).

CSF collection: The lumbar puncture at level L3/L4 or L4/L5 of the spine will be performed by a qualified clinician. The applicants have extensive experience with this procedure (see, e.g., ethic proposals 46/2010 and 404/2010). Subjects will be closely monitored during and after the procedure. Patients need to rest for 30 min after CSF collection and will be informed that occurrence of side effects of this procedure might be interfere with their driving abilities. Up to 15 ml of CSF will be collected unless there is evidence of clinically significant coagulopathy or thrombocytopenia that would interfere with the safe conduct of the procedure. This amount does not represent any health hazard. The first 2 ml of CSF will be processed at the Zentrallabor to conduct standard analyses on cell count, protein, and glucose levels, while another aliquot of 400 µL Liquor will be sent to the Neurochemisches Labor to conduct analyses of neurodegenerative markers such as Abeta1-42 and Abeta1-40.

8.5.2. *Tissue collection*

Not applicable.

8.5.3. *Analysis of biomaterial*

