A structured and integrated exploration of biomaterial in combination with the analysis of the extensive quantitative dataset obtained in this study bears the chance for a better molecular, biochemical, and eventually functional understanding of one of the most debilitating symptoms associated with PD, i.e., cognitive deterioration.

For all patients, DNA, CSF, and plasma were sampled at baseline. Available data will be included into data analysis. This includes genetic information received from DNA analysis by using the NeuroChip, especially information on genetic variants associated with dementia and PD, as well as CSF levels of Abeta1-42, phosphor- and total Tau determined within the frame of the ABC-PD study. In collaboration with the company ADX, represented by [name] and [name], the following baseline CSF biomarkers were provided for further analysis of 200 patients: Abeta1-42, Abeta1-40, Abeta1-38, phosphor Tau 181, NF heavy, neurogranin, BASE-1, and alpha-synuclein.

At time of follow-up, a maximum of 50 PD patients is expected to give a third CSF sampling. Levels of CSF biomarkers indicating cognitive worsening [8, 9, 34-37] will be measured using the solid phase enzyme essays from Fujirebio Germany GmbH: Abeta1-42, Abeta1-40, phosphor- and total Tau. In addition, blood (serum) neurofilament light chain will be analysed in cooperation with [name]. med. [name] of the Universitätsklinikum Dresden.

8.5.4. *Storage of biomaterial*

All samples will be stored at -80°C until use. To maximize confidentiality, all biomarker samples and information associated with the samples will be coded to prevent the exposure of the subjects' information and identity. This coding process allows location and destruction of a sample at the subject's request. In addition, sample information is stored in one secured

electronic database, while biomarker data is stored in an independently secured database on a different computer. No one except the investigators of the UKT will have access to the database to deduce the identity of the patient.

9. Risks and possible adverse reactions, end of the study

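### Section 7 calls every hypothesis a priori and rules out p-value correction, although only one directional hypothesis is stated and Aims 1.1 to 1.3 are open marker screens

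*Combined protocol and SAP*

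**What the plan says.** Section 7 opens its analysis plan with a blanket rule: "All following hypotheses will be tested a priori; no post-hoc corrections of p-values will be conducted". Where that section later speaks of correcting comparisons, it means covariate adjustment in regression models, not multiplicity. No significance level or sidedness is given.

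Section 4.1 states one directional hypothesis: PD-MCI patients with an FAQ quotient above 1.008 are at higher risk of cognitive worsening and PDD than PD-MCI patients at or below it. The aims that follow are open. Aim 1.2, for example, reads "Prediction of progression in cognitive scales according to cognitive, IADL, genetic, and biomarker profiles in blood and CSF". Aims 1.1 and 1.3 have the same form for conversion and for ADL scales. None lists its markers or gives a direction for any of them, and Aims 1.2 and 1.3 do not list their scales.

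The candidate markers appear only in section 8.5. Section 8.5.3 names a CSF panel ("Abeta1-42, Abeta1-40, Abeta1-38, phosphor Tau 181, NF heavy, neurogranin, BASE-1, and alpha-synuclein"), earlier baseline measurements ("CSF levels of Abeta1-42, phosphor- and total Tau determined within the frame of the ABC-PD study") and a serum marker ("blood (serum) neurofilament light chain will be analysed in cooperation with"). Section 8.5.1 gives genes as examples only ("e.g. APOE Genotype, MAPT, COMT, and GBA") and also mentions exploratory proteomics and metabolomics.

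Section 6.1 names cognitive status at follow-up as the primary outcome. Section 7 labels one analysis differently from the rest: "As a post-hoc exploratory analysis to identify which subscore best predicted PDD conversion, ROC curves will be calculated for all FAQ scores".

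**The concern.** Stating a hypothesis in advance does not remove multiplicity, and an aim that lists neither its predictors nor its scales has not been stated in advance in any useful sense. Under the rule as written, a nominally significant marker from an open screen could be reported as an a priori predictor, with the same standing as the one hypothesis the study was built on.

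Conversions are few: 17 to PDD by the first follow-up and, by the plan's own estimate, at most 15 more. With so few events, a marker that crosses the threshold by chance will tend to show an exaggerated effect. Section 3.1 proposes patients with PD-MCI and cognitive IADL impairment as a target group for clinical trials, so readers need to see which result is confirmatory and which comes from a screen.

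**Working it through.** The documents give no alpha, number of tests or error rate, so there is no stated figure to reproduce. The check is what the rule implies under explicit assumptions.

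**Markers (sections 8.5.1 and 8.5.3).** The CSF panel has 8, total Tau adds 1, serum neurofilament light chain adds 1, and 4 genes are named as examples: 8 + 1 + 1 + 4 = 14.

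**Outcomes.**
- Aim 1.1: 2 (conversion to PD-MCI, conversion to PDD).
- Aim 1.2: scales not listed. Counting the tests in section 8.2 by domain gives 3 + 2 + 2 + 4 + 2 = 13; MoCA and MMSE make 15. Trail Making Test Part A (Table 1) would make 16.
- Aim 1.3: scales not listed. Tables 2 and 3 offer 4: FAQ by patient, FAQ by informant, Bayer ADL and the PD ADL scale.

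**Assumptions, none stated in the documents.** Alpha is 0.05 per test, each marker is tested singly against each outcome, and no marker has a true effect.

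**Formulas.** Tests k = markers × outcomes. Expected chance findings = 0.05 × k. Chance of at least one, if tests are independent = 1 − 0.95^k.

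| Outcomes tested | k | Expected | At least one |
|---|---|---|---|
| 2 conversions | 14 × 2 = 28 | 1.4 | 76% |
| plus 4 ADL scales | 14 × 6 = 84 | 4.2 | 99% |
| plus 15 cognitive scales | 14 × 21 = 294 | 14.7 | near 100% |
| plus Trail Making Part A | 14 × 22 = 308 | 15.4 | near 100% |

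**How far this moves.**
- Without serum neurofilament: section 8.5.1 describes its collection at this follow-up, and section 8.5.3 lists the baseline samples as DNA, CSF and plasma, so it may exist only at the outcome visit. Then 13 × 2 = 26 tests, 1.3 expected, 1 − 0.95^26 = 74%.
- CSF markers only, two conversions: 9 × 2 = 18 tests, 0.9 expected, 60%.
- Half the markers truly predictive: the other 7 give 7 × 2 × 0.05 = 0.7 for conversion (51% chance of at least one) and 7 × 21 × 0.05 = 7.35 over 21 outcomes.
- Alpha 0.01 instead: 28 × 0.01 = 0.28 and 294 × 0.01 = 2.94.
- Correlated tests: the expected count is unchanged but its spread widens. In a simulation of the 308-test grid (5,000 runs), the central 95% range was 8 to 23 with independence and 2 to 55 (median 11) when markers and outcomes were each correlated 0.5.

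**The case against.** The strongest reply is that the plan never says markers are tested one at a time. The aims speak of profiles, and the only analysis in section 7 that mentions biomarkers is the logistic model, where they are adjusters for cognitive IADL status. Section 8.5.3 also chooses its CSF markers because they are thought to indicate cognitive worsening, so assuming no true effects is a worst case. Both points stand, and both lower the count. They do not rescue the rule: section 7 also plans linear regression on unspecified predictors of neuropsychological and IADL scores, and the number of tests cannot be determined from the plan.

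A second reply is that an exploratory cohort needs no correction. That would be defensible if the analyses were labelled exploratory, but the plan labels them all a priori.

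A third is that the plan already separates its layers: one directional hypothesis, one primary outcome, and an ROC analysis openly marked as post hoc. This has some force. The ROC step is at most a mild inconsistency with the opening rule, since choosing a score by the Youden index needs no p-value. But naming the outcome fixes neither rater nor model, and nothing marks the marker analyses as secondary.

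A reader might also infer that the 4.1 hypothesis can be tested in 16 ways: two raters, baseline or follow-up IADL, worsening or PDD, Cox or logistic. The documents do not support that product. The logistic model is tied to baseline status, and worsening on scales is handled by linear regression, not by Cox or logistic models. What remains open is the rater, the choice between Cox and logistic regression, and, within the Cox model, baseline or follow-up IADL.

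**Conclusion.** The concern holds as a defect in a stated rule. The plan has one directional hypothesis and several open screens, gives them the same a priori label, and excludes any correction.

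Its size is a range. With alpha 0.05, single-marker tests and no true effects, it runs from about 1.4 chance findings for the two conversion outcomes (about 1.3 without serum neurofilament) to about 15 if every cognitive and ADL scale is tested. Proteomics, metabolomics or further gene variants would raise it.

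A reader might take 15 false predictors as the plain expectation. The documents do not support that: it needs all three assumptions plus about 21 outcomes, most of which come from a count of scales that the aims themselves do not make. The case for change does not rest on the upper figure.

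**What to change.** Replace the opening sentence of the statistics section.

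- **One confirmatory test.** Name the 4.1 contrast: PD-MCI patients, baseline FAQ quotient above 1.008 versus at or below it, conversion to PDD, one pre-named rater, one model, and a stated alpha and sidedness. The rater must be written in, because section 3.2 does not say whose ratings produced the 1.008 cut-off and section 3.1 says both patients and informants rated.
- **Everything else exploratory.** Drop the a priori label for these analyses.
- **Closed families.** List the markers and outcomes that form each aim's family. Without a closed list, false-discovery control cannot be applied.
- **Reporting.** Show Benjamini-Hochberg adjusted p-values, at a level set in advance, beside the nominal ones, and give estimates with confidence intervals for every marker tested, whatever the result.

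The cost is revised wording, a list of markers and scales, and one extra column in the results tables. No new data, visits or patients are needed. The downside is that fewer marker findings can be called significant.

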Results. Of 268 patients with PD assessed at baseline, 108 (40.3%) had PD-MCI. After a period of 3.8 ± 0.8 years, 182 (61.2%) patients were re-assessed and 164 analysed (17 excluded due to deep brain stimulation, one patients without classification of cognitive group). At follow-up, 93 (56.7%) patients fulfilled criteria for normal cognitive function (PD-CN), 54 for PD-MCI (32.9%), and 17 (10.4%) had developed dementia. Predictive ratio of baseline cognitive IADL impairment (n=37; 21.3%) for dementia conversion was descriptively higher than for PD-MCI, but highest in patients with both markers [HR=12.01, 95%-confidence interval (CI): 4.47-32.23]. Nearly half of patients (n=10, 47.6%) with baseline classification of cognitive IADL impairment and PD-MCI converted to dementia. Baseline status of cognitive IADL impairment was associated with higher non-motor burden, worse cognitive performance, and more severe IADL progression over the study period. In a post-hoc Receiver Operating Characteristic (ROC) analysis, the FAQ quotient (cut-off >1.008) was confirmed to best predict conversion to dementia compared to other IADL scores. Only two patients with baseline status of cognitive IADL impairment in our sample scored below the newly identified FAQ quotient cut-off of 1.008 resulting in a total of 35 (21.3%) patients with values above this defined cut-off. The FAQ motor score [AUC(area under the curve)=0.60, 95%-CI: 0.52-0.67, $p=0.13$], reflecting predominantly motor aspects on IADL function, was not associated with PDD conversion.

4. Objectives of the study

Based on previous analyses in the sample we suggest that monitoring of both cognition and cognitive ADL impairment reflect neurodegeneration associated to PDD development. This study evaluates markers predicting cognitive and ADL long-term outcome in our sample. Additionally, we will investigate whether ratings of patients or informants best predicted decline of cognitive impairment and/or everyday function. Clinical data along with other clinical marker and biomarker status will be investigated.

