6.1. Study population

Between March 30th, 2014 and December 31th, 2017, we recruited a large cohort of 268 PD patients within the frame of the "Amyloid-Beta in cerebrospinal fluid as a risk factor for cognitive dysfunction in Parkinson's Disease" (ABC-PD, ethic protocol 686/2013B01) study. Follow-up visits were conducted between July 2018 and September 2020, all patients of the ABC-PD study were contacted for re-examination.

We propose a second follow-up of the already existing longitudinal cohort described above with a longitudinal assessment including neuropsychological in-depth endophenotyping and CSF biomarker analyses. In total 182 patients will be invited to participate in the second

follow-up assessment. If patients are not able to attend a clinical visit in-house, possibility of assessments at patients' homes shall be offered. Moreover, if patients are not able to give consent for study participation (confirmed by an independent physician), the legal guardian will be contacted to give study consent for participation. Legal guardians are defined as persons with legal care directive or lasting power of attorney. For drop-outs different reasons for drop-out will be coded (e.g. deceased, disabled, disinterested/refuse study participation, unable to reach/unknown address).

Diagnosis of cognitive impairment:

Patients were classified as PD-MCI according to Level-II Movement Disorder Society recommendations if cognitive impairment was present but did not significantly interfere with everyday function [25]. PDD was defined according to Movement Disorder Society Task Force criteria [17] if cognitive impairment was present and severe enough to impair ADL function unrelated to motor or autonomic symptoms and at least one behavioral symptom was present to support diagnosis. Cognitive impairment was defined according to Level-I (impairment of global cognition) for patients with minimal assessments, or Level-II (performance below 1.5 standard deviation of the population mean reported in the test manuals on at least two tests) for patients assessed using a full cognitive battery. Patients not meeting either of the diagnostic criteria were classified as PD-CN. Cognitive status at follow-up was defined as the primary study outcome.

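### The all-visits restriction on the Cox models, read literally, discards recorded PDD events and dementia-free follow-up from the baseline-predictor analyses

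*Combined protocol and SAP*

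**What the plan says.** Section 7 (prediction of cognitive progression) introduces the multivariable Cox models with "In patients who completed all visits, the predictive values of baseline/follow-up IADL". The same sentence covers baseline and follow-up predictors. AIC and the "concordance index (C-index) [26] will be used as model fit indices". The logistic, ROC and mixed-model sentences carry no such restriction.

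Aim 1.1 in section 4.1 is "Prediction of conversion rates to PD-MCI (among PD-CN) and PDD (among non-demented patients", according to baseline profiles. Section 6.1 describes three assessments: baseline, a completed first follow-up and the proposed second. Section 6.3 states: "A drop-out rate of 20% is expected for follow-up retention". Section 6.1 adds: "For drop-outs different reasons for drop-out will be coded (e.g. deceased, disabled". Reasons are to be recorded for the analysis, but no method that uses them is given.

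No section says how a conversion is dated or when a patient without conversion is censored, for either endpoint of Aim 1.1.

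**The concern.** For a model with baseline predictors, a PDD diagnosis at first follow-up is a complete observation: time at risk and event are both known. Requiring a later visit adds nothing to it. It makes inclusion depend on attendance after the outcome.

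Two things are at stake. The first is precision, because PDD events are few: 17 so far, and "a maximum of additional 15 converters are expected". The second is selection. Section 3.1 ties PDD to more nursing-home admission and more deaths, and section 6.1 names death and disability among the drop-out reasons. Converters may therefore be less likely to return, and conversion figures drawn from completers would be too low. If non-return also differs by baseline marker, the HR is affected.

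**Working it through.** **Inputs.** Section 3.2: "164 analysed (17 excluded due to deep brain stimulation", one more unclassified; 17 PDD cases; 10 converters with both markers (47.6%, hence 10/0.476 = 21 patients); "HR=12.01, 95%-confidence interval (CI): 4.47-32.23" for both markers. Section 6.3: 20% drop-out, 145 patients. Section 7: mean interval 3.78 years, at most 15 new converters.

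**The plan's own figures.** 182 × 0.80 = 145.6 (stated 145). 145 × 17/164 = 15.0 (stated 15). The second product includes patients already demented. With the 147 non-demented, 147 × 0.80 × 17/164 = 12.2, so fewer than 15 new converters are also considered below.

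**Case 1: loss unrelated to PDD and marker (20% of the 164 analysed).**
- Patients lost: 164 × 0.20 = 32.8.
- Known PDD events lost: 17 × 0.20 = 3.4 (binomial 95% range 1 to 7). Chance of losing at least one: 1 − 0.8^17 = 0.98.
- Of these, from the both-marker converters: 10 × 0.20 = 2.
- Dementia-free time lost: 147 × 0.20 × 3.78 = 111 person-years.
- SE of log HR at 17 events: ln(32.23/4.47)/(2 × 1.96) = 0.504.
- Assumption: SE scales with 1/√events at the same split between groups.

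| New converters | Events, all patients | Events, completers | SE, all | SE, completers | Ratio |
|---|---|---|---|---|---|
| 15 | 32 | 28.6 | 0.367 | 0.389 | 1.06 |
| 10 | 27 | 23.6 | 0.400 | 0.428 | 1.07 |
| 5 | 22 | 18.6 | 0.443 | 0.482 | 1.09 |
| 0 | 17 | 13.6 | 0.504 | 0.563 | 1.12 |

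At HR 12.01 and 15 new converters, the interval goes from 5.8–24.7 to 5.6–25.7.

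**Case 2: loss related to PDD, not to the marker.** The loss rates are assumptions. Overall loss stays at 32.8, leaving 131.2 completers, and 15 new converters are assumed.
- 40% of PDD cases lost: 17 × 0.60 = 10.2 remain. Apparent first-follow-up conversion is 10.2/131.2 = 7.8%, against 17/164 = 10.4%. Total events 25.2; SE ratio √(32/25.2) = 1.13.
- 60% lost: 17 × 0.40 = 6.8 remain. 6.8/131.2 = 5.2%. Total events 21.8; SE ratio √(32/21.8) = 1.21.

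A two-interval grouped Cox model (complementary log-log link, expected counts from 10/21 and 7/143, same HR in both intervals) gives the same SE ratios. Its HR changes by a factor of only 1.03 to 1.05.

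**Case 3: loss related to PDD and marker jointly.** In the same model, losing 60% of both-marker converters and 20% of the others multiplies the HR by 0.80. The reverse split multiplies it by 1.31. Both splits are illustrations, not forecasts.

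**PD-MCI endpoint.** The loss cannot be computed, because the documents do not give the number of PD-CN patients who became PD-MCI.

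**The case against.** - **The phrase may mean only the visits each model needs.** That is possible, and one sentence would settle it. The text does not say so.
- **AIC comparison needs a common patient set, and models starting at first follow-up need the second visit anyway.** Both are true, and this may be the motive. A common set can be formed for those comparisons without dropping known events from every baseline-predictor model.
- **The cost is small.** In Case 1 it is: an interval of 5.6–25.7 leads to the same conclusion as 5.8–24.7, and the stated power figures concern the mixed models, not the Cox models. That rests on loss being unrelated to PDD and marker, which no section states.
- **First-interval data are not lost to the programme.** Correct. Section 3.2 already reports an HR from them, and the logistic, ROC and mixed-model sentences are unrestricted. A reader might infer that the recorded events vanish from the whole analysis; the text limits the problem to the Cox models.
- **The plan works to limit loss.** Section 6.1 offers home visits and guardian consent, and section 8.1 brings in routine-care data. These may reduce differential loss, but they do not lift the restriction. The reach of guardian consent is also unclear, because section 6.2.2 excludes disability that prevents consent.

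**Conclusion.** The point holds for Cox models with baseline predictors, under the literal reading. The stated rule discards usable events and follow-up, and no other section supplies a censoring rule.

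Its size depends on who fails to return. With 20% loss unrelated to PDD and marker, about 3.4 of 17 known events go, the SE rises 6% to 12%, and the HR is unbiased. With PDD-related loss, conversion figures under Aim 1.1 are biased downward. At an assumed 40–60% loss of PDD cases, 10.4% becomes 7.8–5.2% and the SE rises about 13% to 21%, while the HR barely moves. With loss that also depends on the marker, the HR can be biased in either direction.

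A reader might infer that the HR will be biased, or that the Cox analysis is invalid. The documents do not support that: they make PDD-related loss plausible but give no return rates by PDD status or marker. Nor do they support the opposite inference, that only a little precision is at risk. The figures also assume that the 20% applies to the 164 analysed patients. The point should be fixed before analysis.

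**What to change.** For models with baseline predictors, replace the restriction with wording such as:

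> *All patients at risk at baseline (non-demented for the PDD endpoint; PD-CN for the PD-MCI endpoint) with at least one follow-up cognitive assessment. The event is counted at the visit of first diagnosis, regardless of later attendance. Event-free patients are censored at their last cognitive assessment. Death before conversion is a competing event when conversion rates are estimated. Models with first-follow-up predictors start at first follow-up, in patients still at risk. AIC and C-index are compared only between models fitted to the same patients and outcome.*

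Add an interval-censored sensitivity analysis, since the first interval ranged from 1.67 to 5.79 years. Keep the completer analysis as a further sensitivity analysis. Report, by baseline marker group, how many first-follow-up converters did and did not return; this would show whether loss was differential.

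The cost is SAP wording and a little programming, as the first-follow-up diagnoses are already held. Follow-up becomes unequal, censoring of event-free drop-outs must be assumed non-informative, and AIC comparisons across predictor time points need a common subset. Selection through the 86 patients never re-assessed (268 − 182) remains.
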